### 8.6.2.1. Immune-related Response Criteria (irRC)

Tumor response is based on total measurable of tumor burden in patients with solid tumors (non-AML patients). For the irRC, index and measurable new lesions are taken into account. A measurable lesion is defined as 5x5 mm or more on helical Computed Tomography (CT) scan.

At the pretreatment tumor assessment, the sum of the products of the 2 largest perpendicular diameters (SPD) of all index lesions (up to 5 lesions per organ, up to 10 visceral lesions, and 5 cutaneous index lesions) is calculated.

At each subsequent tumor assessment, the SPD of the index lesions and of new, measurable lesions ( $\geq 5x5$  mm, up to 5 new lesions per organ; 5 new cutaneous lesions; and 10 visceral lesions) are added together to provide the total tumor burden:

Tumor Burden =  $SPD_{index \ lesions} + SPD_{new, \ measurable \ lesions}$ 

Percentage changes in tumor burden per assessment time point describe the size and growth of both baseline and new, measurable lesions as they appear. At each tumor assessment, the response in index and new, measurable lesions is defined based on the change in tumor burden (after ruling out immune-related progressive disease [irPD]). Decreases in tumor burden must be assessed relative to pretreatment measurements (i.e. the SPD of all index lesions at screening).

Overall response will be determined by the investigator based on tumor burden according to the irRC response assessments as follows:

- irCR (immune-related complete response) = complete disappearance of all lesion (whether measurable or not, and no new lesions) confirmed by a repeat consecutive assessment 4 weeks after the date of first documentation
- irPR (immune-related partial response) = decrease in tumor burden  $\geq 50\%$  relative to baseline confirmed by a consecutive assessment 4 weeks after the date of first documentation
- irSD (immune-related stable disease) = not meeting criteria for irCR or irPR and the absence of irPD
- irPD (immune-related progressive disease) = increase in tumor burden ≥ 25% relative to nadir (prior minimum recorded tumor burden during the study) confirmed by a repeat, consecutive assessment at least 4 weeks after the date of first documentation

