- Unconfirmed irPD = Any irPD record after study day 1 and no record of irPD confirmed 4 weeks after, which include the situation that the PI can discontinue a patient from the study for the reason of PD without confirmation of PD after 4 weeks if patients have rapid symptomatic progression accompanied by a decline in performance status.

The assessment made by the investigator will be used for all summaries.

Best response is defined to be the best irRC response (irCR > irPR > irSD > irPD) evaluated after dosing until treatment discontinuation. Patients without post-baseline evaluations will be considered as unevaluable. Additional categories are defined for response (irCR + irPR) and disease control (irCR + irPR + irSD).

Tables will summarize the number and percentage of the best overall tumor response for each category by dose cohort, the number, percentage, and Wilson Score 95% CI will also be presented for the response categories of irCR, response, and disease control.

The percent change in tumor burden from baseline will be presented at each posttreatment tumor assessment graphically and in patient data listings. Percent change will be calculated as 100\*[(current tumor burden - baseline tumor burden)/baseline tumor burden]. The best change, i.e., the minimum of percent change from baseline for each patient will be displayed in a waterfall plot.

A by-patient listing of irRC assessment will be provided.

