## 8.6.4. Additional Exploratory Endpoints

For solid tumor patients the following endpoints will be calculated as follows:

• Progression-free survival (PFS) is defined as the time in weeks from first dose date to the date of progression or the date of death due to any cause. Patients who are alive and have not progressed by the date of analysis data cut-off will be censored at the last free evaluable tumor assessment date based on investigator

assessment. Patients with missing protocol scheduled tumor assessment(s) prior to radiologic disease progression will be considered as having disease progression on the date of the actual assessment of disease progression.

- Time to progression (TTP) is defined as the time in weeks from first dose date to the date of observed disease progression. Patients who do not have disease progression by the date of analysis data cutoff will be censored at the date of last evaluable tumor assessment based on investigator assessment.
- Duration of response (DOR) is defined as the time in weeks from the first date of response to date of first progression of disease or death in the subset of patients with an objective response of irCR or irPR. Patients who respond and have not progressed (as evaluated by investigator assessment) while on study or die will be censored at the date of their last evaluable tumor assessment. Duration of response is calculated only for patients with an objective response.

For AML patients, the following endpoints will be calculated as follows:

- Relapse is defined as
  - an investigator assessment following CRc becoming PR, PRi, PD, or No Response. The date of the worsening disease assessment will be the relapse date; or
  - an investigator assessment following PR or PRi becoming PD or No Response. The date of the worsening disease assessment will be the relapse date
- Duration of CRc: Time, in weeks, from first CRc until documented relapse and is only defined for patients who achieve CRc. Patients who die without report of relapse are considered non-events and censored at their last relapse-free disease assessment date. Patients who come off study for an allogeneic HSCT will be considered non-events and censored at the time of treatment discontinuation. Other patients who do not relapse on study are considered non-events and censored at the last relapse-free assessment date.

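### SAP 8.6.2.1 defines unconfirmed irPD but gives it no place in best response, and 8.6.4 does not say whether it is a PFS, TTP or DOR event, so such a patient can be read as stable disease or left unclassified

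*SAP*

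**What the plan says.** SAP 8.6.2.1 lists the investigator's response categories for solid tumors.

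- irPD is a rise in tumor burden of at least 25% over nadir, "confirmed by a repeat, consecutive assessment at least 4 weeks after the date of first documentation".
- Stable disease is what remains: "irSD (immune-related stable disease) = not meeting criteria for irCR or irPR and the absence of irPD".
- A separate bullet follows: "Unconfirmed irPD = Any irPD record after study day 1 and no record of irPD confirmed 4 weeks after". It expressly takes in patients whom the investigator discontinues for fast symptomatic worsening with falling performance status.

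The same section then sets the ranking: "Best response is defined to be the best irRC response (irCR > irPR > irSD > irPD) evaluated after dosing until treatment discontinuation". Disease control is the sum of irCR, irPR and irSD, reported by dose cohort with a Wilson 95% interval. The investigator's assessment is used for all summaries.

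For PFS, SAP 8.6.4 reads: "defined as the time in weeks from first dose date to the date of progression or the date of death due to any cause". TTP runs to observed progression, and DOR to first progression or death. None of the three mentions confirmation.

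The tumor-assessment footnotes to Tables 1 to 4 (SAP 6.1) require a repeat assessment at least 4 weeks later for progressive disease, with an exception for rapid clinical deterioration. For glioblastoma they also ask for further imaging or pathology to separate progression from pseudoprogression.

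**The concern.** A defined outcome has no place in the table that is meant to hold every outcome. The AML section (8.6.2.2) avoids this: its ranking runs through every defined on-treatment category, down to No Response and Missing.

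The patients concerned are not a random subset. Someone who deteriorates quickly is the least likely to return for a confirming scan. If these patients enter disease control, the reported rate moves toward apparent benefit. If they are non-events for TTP, they are censored because they were progressing, so the censoring is informative. The study is open-label and response is investigator-assessed. A mapping chosen after the data are seen would be hard to defend.

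**Working it through.** **1. Where the category can go.** SAP 8.3 puts non-AML patients with measurable lesions and at least one post-treatment assessment in the irRC population. These patients have a post-baseline evaluation, so the unevaluable class in 8.6.2.1 does not fit them. The possible placements are:

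| Reading | Support in the text | Difficulty |
|---|---|---|
| irSD, inside disease control | irPD as defined needs confirmation, so the condition "not meeting criteria for irCR or irPR and the absence of irPD" can be met | The unconfirmed bullet itself speaks of "Any irPD record after study day 1 and no record of irPD confirmed 4 weeks after", so irPD is arguably not absent |
| Own category, outside disease control | It has its own bullet, and disease control names only irCR, irPR and irSD | It has no rank, so no best response follows |
| Pooled with irPD | The word irPD is used for the record | Contradicts the confirmation clause |

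No sentence chooses among them.

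**2. How easily the case arises.** SAP Section 2 lets patients stay on drug until progression is confirmed, so the case mainly concerns patients stopped at the first irPD. Take nominal days and a patient stopped on the Day 57 pre-dose scan, with End of Study due within 28 days of the last dose:

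- Part 1: last dose Day 43, End of Study by Day 43 + 28 = Day 71, which is 71 - 57 = 14 days after the scan.
- Part 2: last dose Day 50, End of Study by Day 50 + 28 = Day 78, which is 78 - 57 = 21 days after the scan.

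Both fall short of 4 weeks (28 days). Any later confirmation lies beyond treatment discontinuation, where the best-response window closes.

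**3. Effect on disease control.** The plan states no rate to reproduce. Assumptions: n = 10 (the size of one RP2D tumor-type cohort, SAP 4.1), 3 patients truly controlled, and 0 to 3 patients with unconfirmed irPD only. The interval is the standard Wilson score with z = 1.96, z² = 3.84:

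(2np + z² ± z√(z² + 4npq)) / (2(n + z²))

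- 3/10: (6 + 3.84 ± 1.96√(3.84 + 8.4)) / 27.68 = 0.108 to 0.603
- 6/10: (12 + 3.84 ± 1.96√(3.84 + 9.6)) / 27.68 = 0.313 to 0.832

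| Unconfirmed only | Not control | Read as irSD | Dropped from denominator |
|---|---|---|---|
| 0 | 30% (10.8-60.3) | 30% (10.8-60.3) | 30% (10.8-60.3) |
| 1 | 30% | 40% (16.8-68.7) | 3/9 = 33.3% (12.1-64.6) |
| 2 | 30% | 50% (23.7-76.3) | 3/8 = 37.5% (13.7-69.4) |
| 3 | 30% | 60% (31.3-83.2) | 3/7 = 42.9% (15.8-75.0) |

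Each patient read as irSD moves the rate by 100/n points: 16.7 at n = 6, 10 at n = 10, and 3.3 at n = 30 (three RP2D cohorts pooled at one starting dose).

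**4. Effect on time to event.** Hypothetical cohort of 10: four with unconfirmed irPD at week 8, the other six with events at weeks 8, 16, 16, 24, 32 and 40.

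- Unconfirmed irPD is an event: 5 of 10 fail at week 8, so the curve reaches 0.5 at week 8 (10 events in all).
- Censored at week 8 (the last evaluable assessment, as TTP is worded): S(8) = 9/10 = 0.90; S(16) = 0.90 × 3/5 = 0.54; S(24) = 0.54 × 2/3 = 0.36. The median is week 24 (6 events).
- Censored at day 1, because no progression-free post-baseline scan exists (one reading of the PFS censoring rule): S(8) = 5/6; S(16) = 5/6 × 3/5 = 0.50. The curve reaches 0.5 at week 16 (6 events).

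**5. The two statements on rapid progression.** The footnotes to Tables 1 to 4 imply that progression with rapid deterioration counts without a repeat scan. Section 8.6.2.1 puts the same situation under unconfirmed irPD. Section 8.6.4 does not say which statement governs the endpoints.

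**The case against.** A reader might infer that the SAP literally classes these patients as irSD and so inflates disease control. The documents do not establish that. The separate bullet, its use of the term irPD for the unconfirmed record, and the instruction to assign response once irPD has been excluded all support a row outside disease control. Being unranked and being irSD are also alternatives: an unranked patient inflates nothing. That part of the objection stands, so inflation is a risk and not a stated result.

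A reader might likewise infer that the fastest progressors are censored for TTP. The footnote exception and the wording about observed progression both point the other way. Informative censoring follows only if these patients are treated as non-events. Death remains a PFS event whatever the scan shows.

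The investigator's assessment governs, and an investigator who withdraws a patient for progression is unlikely to record irSD. This lowers the chance of the worst reading, but it says who assesses, not how an unconfirmed record becomes a best response.

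The direction of error is not guaranteed either. In glioblastoma, counting a single last irPD scan as an event may count pseudoprogression.

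By-patient irRC and time-to-event listings and the waterfall plot would make these patients visible. The protocol text available is the amendment history, so a mapping in the body of protocol version 7 cannot be excluded. The SAP would still need to carry it into its ranking and event definitions.

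**Conclusion.** The gap is real and bounded. Unconfirmed irPD is defined but not ranked, its event status and date are not set for PFS, TTP or DOR, and two parts of the SAP treat rapid progression differently.

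For best response, only solid-tumor patients with no earlier irSD, irPR or irCR are exposed; irSD at week 8 followed by unconfirmed irPD at week 16 is irSD on every reading. For the time-to-event endpoints, any solid-tumor patient with unconfirmed irPD is exposed. Response is secondary and time to event is exploratory; the DLT and MTD analysis does not depend on either.

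The size rests on an assumed count. With 3 such patients in 10, disease control ranges from 30% to 60% by reading alone; with none, nothing changes. The shift in the median from week 8 to week 24 comes from an invented cohort and shows only that the choice can matter.

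**What to change.** Amend the SAP before database lock:

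- **Best response.** Rank irCR > irPR > irSD > unconfirmed irPD > irPD. Show unconfirmed irPD as its own row, keep it in the denominator, and state that it is not disease control.
- **PFS, TTP and DOR.** Date progression at first documentation of irPD when it is confirmed, or when it is the patient's last assessment or the patient discontinued for progression. Do not count irPD that a later assessment fails to confirm.
- **Consistency.** Reconcile the rapid-progression text in 8.6.2.1 with the footnotes to Tables 1 to 4, and have 8.6.4 refer to the agreed wording.
- **Sensitivity.** Repeat PFS, TTP and DOR counting only confirmed irPD, because of pseudoprogression in glioblastoma.

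The cost is SAP wording and derivation code; no new data are needed. The disease control rate may be slightly lower, and the main time-to-event analysis may count some pseudoprogression as events, which the sensitivity analysis would show. Ranking unconfirmed above confirmed irPD is a convention; what matters is that the rank is fixed in advance and lies below irSD.

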# 8.6.2.2. Modified International Working Group response criteria in acute myeloid leukemia (IWG)

The modified International Working Group (IWG) response criteria were developed to assess the activity of drugs in AML. The criteria are as follows:

- CR: Complete remission
  - o Morphologic CR
    - < 5% Marrow blasts in an aspirate with spicules patient independent of transfusions,

    - Absolute neutrophil count > 1000/µL
    - Platelets  $> 100,000/\mu L$
    - No residual evidence of extramedullary disease
  - Cytogenetic CR cytogenetics normal (in patients with previously abnormal cytogenetics)
  - o Molecular CR molecular studies negative
- CRi: < 5% marrow blasts but with persistence of cytopenias (ie, absolute neutrophil count  $< 1000 / \mu L$  and/or platelets  $< 100,000 / \mu L$ )
- PR: Partial remission. Decrease of at least 50% in the percentage of blasts to 5% to 25% in the bone marrow aspirate and the normalization of blood counts, as noted above.
- PRi: Decrease of at least 50% in the percentage of blasts to 5% to 25% in the bone marrow aspirate but with persistence of cytopenias (ie, absolute neutrophil count < 1000 /µL and/or platelets < 100,000/µL).
- PD: Progressive disease. An increase of at least 50% in the percentage of blasts in the bone marrow aspirate with an increase of at least 10% of blasts in the bone marrow.

• No Response: None of the above criteria is met. This typically would represent patients that are refractory to treatment prior to achieving response or prior to treatment discontinuation.

Measurable disease will be defined as >5% marrow blasts. The assessment made by the investigator will be used for all summaries.

Best remission is defined to be the best measured remission status by disease assessment (Molecular CR > Cytogenetic CR > Morphologic CR > CRi > PR > PRi > PD > No Response > Missing). Other categories are defined for CRc (CR + CRi) and disease control (CR + CRi + PR + PRi). The number and percentage for best response will be presented and the number, percentage, and Wilson Score 95% CI will also be presented for the categories of CR, CRc, and disease control. A shift table will be presented between baseline response and best response on-treatment. The order of the best response on-treatment will be Molecular CR > Cytogenetic CR > Morphologic CR > CRi > PR > PRi > PD > No Response > Missing. And the response of baseline will be classified as Molecular CR, Cytogenetic CR, Morphologic CR, CRi, Stable disease (SD). Patients who are not classified in any of Molecular CR, Cytogenetic CR, Morphologic CR or CRi will be classified as stable disease (SD). If a patient could be classified in multiple categories at baseline, the response will be chosen in the following order: Molecular CR > Cytogenetic CR > Morphologic CR > CRi > SD. All summaries will be presented overall and by dose cohort.

A by-patient listing of IWG assessment will be provided.

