# 2. INTRODUCTION

This statistical analysis plan (SAP) describes the statistical methods to be used during the reporting and analyses of data collected under Sunovion Pharmaceuticals Inc. Protocol D8350004, "Initial Phase 1 Study of WT2725 Dosing Emulsion in Patients with Advanced Malignancies".

This is a Phase 1, open-label, dose-escalation study in adult patients with advanced malignancies known to overexpress the Wilms' tumor gene 1 (WT1) protein. The study will primarily evaluate dosing-limiting toxicity (DLT) and define the maximum tolerated dose (MTD) of WT2725 Dosing Emulsion during the DLT Evaluation Period. Patients may remain on study drug until confirmed progressive disease, intolerance to treatment with study drug, or fulfillment of any of the other criteria for discontinuation. The primary endpoints will be based on the occurrence of DLT and adverse events (AEs), and the findings from clinical laboratory tests, vital signs measurements, body weight measurements, and electrocardiogram (ECG) results.

This SAP should be read in conjunction with the study protocol version 7 (December 3rd, 2014) and case report form (CRF) dated January 26th, 2015..

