# 6.3. Secondary Endpoint Variables

- Proportion of patients in each overall response category for each dose cohort based on irRC, modified IWG, and/or tumor markers, as appropriate, for all posttreatment tumor assessments.
- Percent change in tumor burden from baseline to each posttreatment tumor assessment and the last tumor assessment for each dose cohort.
- The amount of immune response evaluated by:
  - Measurement in peripheral blood of WT1 peptide-specific Cytotoxic T lymphocyte (CTL) induction activity at each assessment time.
  - Measurement in peripheral blood of WT1 serum antibody titer at each assessment time.
  - o DTH to the WT2725 peptide at each assessment time.
  - Measurement of level of expression of CD8+, Foxp3, human leukocyte antigen (HLA) class I, and WT1 protein in tumor tissue using immunohistochemistry (IHC) methods

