## 8.3. Analysis Populations

There are 3 planned analysis populations.

- Safety population: includes all enrolled patients who receive at least 1 dose of study drug and will be used for the analysis of all safety and efficacy data except as noted below
- DLT population: includes all patients in the Safety population who experience a DLT within the DLT evaluation period or completed the DLT evaluation without experiencing a DLT and will be used for analysis of DLT.
- Efficacy population: include all patients in the Safety population who are evaluable for response (for each irRC, IWG, CA-125 and WT1 by RT-PCR)
  - o Population for irRC response: including all the patients in the Safety population who are not AML patients and whose lesions are measureable and have at least one posttreatment assessment. (Note that any posttreatment irRC assessment is based on the baseline assessment)
  - O Population for modified IWG response: includes all the AML patients in the Safety population who have >5% marrow blasts or >50 copy/μ g RNA of quantitative RT-PCR for WT1 transcript before the first date/time of study drug and who have at least one posttreatment assessment.
  - o Population for CA-125 tumor marker: including all ovarian cancer patients in the Safety population who have a baseline CA-125 assessment and at least one assessment posttreatment.
  - Population for WT1 by RT-PCR tumor marker: includes AML patients in the Safety population who have a baseline assessment and at least one assessment posttreatment.
- Population for CTL: including all patients in the Safety population who has a baseline assessment of percentages of WT1-positive cells among CD8-positive cells and at least one post-baseline assessment

Additional populations for analyses of other tumor markers identified may be defined in a similar manner.

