#### 8.6.2.3. Tumor Markers

CA-125 and WT1 by RT-PCR will be summarized for only ovarian cancer and AML patients, respectively. Additional tumor markers may be identified and summarized as appropriate.

To evaluate the response according to CA-125, the definition of response described in Rustin, et al. [Rustin-2011] will be used. A response according to CA-125 has occurred if there is at least a 50% reduction in CA-125 levels from baseline sample. This response must be confirmed at least 28 days later by a repeat assessment that is a at least a 50% reduction or is within 10% ( $\pm$  10%) using the same assay method. Additionally, the baseline must be at least 2 times the upper limit of normal and drawn within 4 weeks prior to first dose date. Progression is defined as an increase of 2 times the nadir value at any time. If the nadir is less than the upper limit of normal then a progression will be declared at 2 times the upper limit of normal. This must be confirmed at least one week

later. Not-response/Non-PD will be assessed if neither the criteria of response or progression are achieved. A table will present the number and percentage of patients for their best response (response>Not-response/Non-PD>progression) for the CA-125 population. Additionally, the percent change from baseline may be presented over time graphically.

The descriptive statistics for the log transformed RT-PCR value will be presented for bone marrow and blood separately by each assessment and by different cohort. For any assessment, if there are multiple assessments within each category (either bone marrow or blood), choose the highest one. If the result of RT-PCR is undetectable, impute it as half of  $5.0 \times 10 \text{ copy}/\mu g$  RNA. The percent change from baseline will be presented over time graphically for WT1 by RT-PCR for the log transformed RT-PCT values.

Additionally, other markers identified upon review may be summarized and/or categorized according to standard criteria.

A by-patient listing for both CA-125, WT1 by RT-PCR, and other tumor markers identified will be provided separately.

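### Both AML best-response orders in SAP 8.6.2.2 rank progressive disease above No Response; the two should be swapped, and only those two table rows are affected

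*SAP*

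**What the plan says.** SAP Section 8.6.2 plans tables of best response on study by dose cohort. For AML, Section 8.6.2.2 selects the best status from a ranked list given twice, once for best remission and once for on-treatment response in the shift table. Both lists end "CRi > PR > PRi > PD > No Response > Missing".

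The same section lists the criteria in the order CR, CRi, PR, PRi, PD, and then gives the residual class: "No Response: None of the above criteria is met". It adds that this class would typically hold patients refractory to treatment.

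The SAP's other two best-response orders are:
- Solid tumors (8.6.2.1): "irCR > irPR > irSD > irPD".
- CA-125 (8.6.2.3): "response>Not-response/Non-PD>progression".

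Wilson intervals for AML are planned for CR, CRc (CR + CRi) and disease control (CR + CRi + PR + PRi). Summaries are overall and by dose cohort, and a by-patient listing is planned.

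**The concern.** A list that selects the best status should place a worse state below a better one. By the SAP's own definition, a No Response assessment is one at which PD was not met. Ranking PD above it means that a later progression replaces an earlier non-progressing assessment as the patient's best result.

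The course is plausible. Section 2 says "Patients may remain on study drug until confirmed progressive disease", so a patient without a response can be assessed again and then progress. The AML tables would count that patient under PD, and a reader would take it that the patient never had a better assessment. The split between PD and No Response in two pre-specified descriptive tables is at stake.

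**Working it through.** The plan states no rate or sample-size figure to reproduce. The check applies the two orders to possible assessment histories and then sizes one affected patient.

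**Step 1. The three orders side by side (SAP 8.6.2.1 to 8.6.2.3).**

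| Criteria | Class meeting neither response nor progression | Where progression ranks |
|---|---|---|
| irRC | irSD | below irSD |
| CA-125 | Not-response/Non-PD | below it |
| Modified IWG | No Response | above No Response |

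AML is the only set with progression above its residual class. The SAP gives no reason for the difference.

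**Step 2. Apply both orders to example histories.**

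| Assessments | Best, as written | Best, PD and No Response swapped |
|---|---|---|
| No Response, No Response, PD | PD | No Response |
| No Response only | No Response | No Response |
| PD only | PD | PD |
| PRi, No Response, PD | PRi | PRi |
| CRi, PD | CRi | CRi |

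**Step 3. Scope.** The list has nine ranks, so four assessments give 9^4 = 6,561 ordered histories. The swap matters only when PD and No Response both occur and nothing better does. Histories using only PD, No Response and Missing number 3^4 = 81. Of these, 2^4 = 16 lack PD, 2^4 = 16 lack No Response, and 1 lacks both. The affected number is 81 − 16 − 16 + 1 = 50, and all 50 move from PD to No Response. This describes which histories change; it is not a probability.

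**Step 4. What cannot move.** CR, CRc and disease control are built from CR, CRi, PR and PRi, all ranked above both swapped classes. The IWG population (8.3) does not depend on best response. Numerators, denominators and Wilson intervals therefore stay the same. AML time to progression (8.6.4) runs to the date of observed progression and does not use best response.

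**Step 5. Size of one count.** Section 4.1 requires at least 6 evaluable patients of each tumor type in Part 1 and at least 4 AML patients at each of two Part 2 dose levels: 6 + 4 + 4 = 14. Assuming all 14 are in the IWG population, one patient is 1/14 = 7.1 points. In a Part 2 cohort with 4 AML patients it is 1/4 = 25 points. If one of the optional expansion cohorts of 10 were AML (an assumption), the total would be 14 + 10 = 24, or 6 + 10 + 6 + 6 = 28 with six AML patients at each Part 2 level. One patient is then 1/24 = 4.2 or 1/28 = 3.6 points.

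**The case against.** The strongest reply is that No Response is a residual failure class and not stable disease. The SAP says it typically holds refractory patients, leaves it out of AML disease control (irSD counts toward solid-tumor disease control), and treats a fall from PR or PRi to either PD or No Response as relapse. All of that stands. A reader might infer that the SAP reports one and the same course in opposite ways for solid tumors and AML. That goes too far, because irSD and No Response are not equivalent. It does not rescue the ranking: both classes lie outside disease control, but only one means that progression criteria were met.

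The reach is also small. PD under these criteria is defined on marrow aspirate, and the schedule footnotes call for marrow when clinically indicated, so few patients may have both assessments. The by-patient listing shows the full sequence. The endpoint in Section 6.3, "Proportion of patients in each overall response category for each dose cohort", goes on to refer to all posttreatment assessments; read by assessment, ranking does not touch it. The affected output is the best-response table planned in 8.6.2.

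A reader might further infer that the AML rates need a separate analysis with intervals for patients not in remission at entry. Section 8.3 admits AML patients "who have >5% marrow blasts or >50 copy" of WT1 transcript, and 8.6.2.2 says "And the response of baseline will be classified as Molecular CR, Cytogenetic CR, Morphologic CR, CRi, Stable disease (SD". But the shift table already gives the counts in the baseline SD row, from which a rate and interval follow. The durations in 8.6.4 cover patients who achieve remission, most naturally read as on study.

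**Conclusion.** The ranking is wrong as written, with minor reach. It misplaces patients who have both a No Response and a PD assessment and nothing better, and it affects only the PD and No Response rows of the AML best-response and shift tables. Each such patient is worth 7.1 points if the overall AML denominator is 14, and less with more AML patients. The total effect is unknown, because the documents do not say how many patients follow that course; with none, the tables are unchanged.

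The documents do not support reading this as an error in the AML remission or disease-control rates, their intervals, the time-to-event results or the DLT/MTD analysis. They also do not show that a baseline-SD response rate is missing in any way that matters. The one loose end on baseline remission is that 8.6.4 does not say outright whether it counts toward the durations. Confidence in the textual point is high.

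**What to change.** In both lists of SAP 8.6.2.2, place No Response directly above PD, leaving the ranks from Molecular CR down to PRi as they are, so that the tail runs PRi, No Response, PD, Missing. This is a wording and programming change that needs no new data. One consequence should be understood: the PD row will then hold only patients with no No Response or better assessment. Progression itself remains visible in the listing and in time to progression.

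Optionally, add a sentence to 8.6.4 saying whether a remission present at baseline counts for duration of CRc and duration of disease control, and from what date. Extra baseline-SD rates are not needed. The durations should not be restricted to patients with baseline SD, since that would drop a patient who enters in CR or CRi, relapses and regains remission on study.
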